7.2. General Methodology

Descriptive statistics will be used to summarize the patient demographic and clinical characteristics at baseline. Data for qualitative variables will be presented as prevalence rates (total number of subjects, number of events, and percent). Data for continuous variables will be summarized using measures of central tendency and dispersion.

During the study all movement data is continuously collected. The primary endpoint for this study are the gait parameters obtained from the Reveal LINQ – REEF Research System, Rev 1.0 (accelerometer) and the

external reference system (i.e. validation accelerometer and/or computer assisted rehabilitation system). All data processing will be performed offline.

7.3. Center Pooling

Since this is a single center study this section is not applicable.

7.4. Handling of Missing, Unused, and Spurious Data and Dropouts

Missing data will not be imputed. The number included in each analysis will be reported so that the reader can assess the potential impact of missing data.

7.5. Adjustments for Multiple Comparisons

No adjustments for multiple comparisons or multiple look at data will be performed.

7.6. Demographic and Other Baseline Characteristics

Descriptive statistics will be used to summarize demographic and baseline characteristic variables for Analysis Population. This will include mean, standard deviation, median, minimum, and maximum for continuous variables, and counts and percentages for categorical variables.

Demographic and Baseline variables will be collected through a password protected excel file database and described with Tables, Listings and Figures as appropriate.

7.7. Treatment Characteristics

Since the study procedures consist in performing the above mentioned exercises during a single session, this section is not applicable.

7.8. Interim Analyses

Interim analyses are not planned for this study.

7.9. Evaluation of Objectives

No formal statistical hypothesis will be tested.

The gait speed (and additional parameters) will be calculated from the Reveal LINQ accelerometer signals, from the validation accelerometer and/or from the computer assisted rehabilitation system. Correlation coefficients between the Reveal LINQ parameters and those from the reference system will be calculated for each maneuver (4MGS, FTSTS, ETGUG and 6MHW). The agreement between the Reveal LINQ derived parameters and the reference parameters will be reported and visualized using

Bland and Altman plots. The agreement between the parameters derived during the different maneuvers will also be evaluated using correlation coefficients and Bland-Altman plots.

Additional exploratory analyses of the data will be conducted as deemed appropriate.

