## **C.2 Clinical endpoints**

The endpoints to be measured during the study are the following:

- ETGUG phase data
- FTSTS timing
- Gait speed (4MGS test)
- Number of steps in 6 minutes (6MW test)
- Distance covered in 6 minutes (6MW test)
- Gait parameters from vertical acceleration axis
- Stand up phase slope
- HRV response to postural change

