### **F.3 Walking exercises**

No devices are implanted in this study. Before the Walking protocol is initiated the RAMware will be downloaded onto the device via the 2090 programmer.

At the beginning of the walking exercises:

- The Reveal LINQ memory will be cleared
- The Reveal LINQ, the accelerometers and the DR220 Holter monitor will be placed on the subject. A medical-grade adhesive will be placed underneath the Reveal LINQ as an additional safety measure aiming to avoid direct contact with the patient's skin
- Time will be recorded;

- The Reveal LINQ and the Actigraph will be manually tapped simultaneously to provide a marker for the further data analysis;

The following exercises will be performed:

- Six Minute Walk (6MW) Test

The 6MW test measures the distance an individual is able to walk over a total of six minutes on a flat surface. The goal is for the individual to walk as far as possible in six minutes. The 6MW test will be performed within the CAREN system environment

- 4 Meter Gait Speed (4MGS) Test

The 4MGS test measures the gait speed an individual is able to walk over 4 meters on a flat surface. The goal is for the individual to walk as fast as possible over 4 meters.

It will be repeated 3 times within the aforementioned 6MW test (after approximately 1, 3 and 5 minutes) to get variability due to subject tiredness. The test will be performed within the CAREN system environment.

- Five Times Sit to Stand (FTSTS) Test

The STS test measures the time a subject takes to stand up from an armchair 5 times in a row, without stopping in between. It is a short test which measures dynamic balance and functional mobility.

- Expanded Timed Get-Up-and-Go (ETGUG) Test

The ETGUG test measures the time it takes a subject to stand up from an armchair, walk a distance of 10 m, turn, walk back to the chair, and sit down. It is a short test of basic mobility skills for frail community-dwelling elderly.

To minimize potential bias due to subject tiredness and fatigue during the execution of the physical tests:

- The order of the tests will be randomly defined at discretion of the investigator;
- A resting time between tests may be granted, at discretion of the investigator.

The tests may or may not be conducted by the same investigator.

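### Does the one-sentence plan for comparing the walking tests with each other need its parameters, pairs, device and 4 m repeats spelled out?

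*SAP*

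**What the plan says.** The four maneuvers are the 4 m gait speed test (4MGS), the six-minute walk (6MW), five times sit to stand (FTSTS) and the expanded timed get-up-and-go (ETGUG). For the main comparison, SAP 7.9 states: "Correlation coefficients between the Reveal LINQ parameters and those from the reference system will be calculated for each maneuver". It adds Bland-Altman plots of LINQ against reference. It then turns to comparison across tests: "The agreement between the parameters derived during the different maneuvers will also be evaluated using correlation coefficients and Bland-Altman plots". Protocol H.1 carries the same text and adds no detail. Gait speed is the only parameter named in SAP 7.9; other parameters are mentioned without a list.

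Protocol C.2 lists the endpoints. Some belong to one test, such as 4MGS gait speed or 6MW distance. Others are tied to none, such as "Gait parameters from vertical acceleration axis" and "Stand up phase slope".

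Protocol F.3 describes the tests. For the 4MGS, "The goal is for the individual to walk as fast as possible over 4 meters". For the 6MW, "The goal is for the individual to walk as far as possible in six minutes". In the ETGUG the subject stands up, must "walk a distance of 10 m, turn, walk back to the chair, and sit down". The 4MGS is done three times inside the 6MW, at about 1, 3 and 5 minutes, "to get variability due to subject tiredness". Both of those tests take place in the CAREN system, which includes a treadmill. FTSTS and ETGUG are not placed there.

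Protocol C.3 and SAP 7.9 say that no formal hypothesis is tested. SAP 6 gives about 20 subjects.

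**The concern.** Bland-Altman analysis needs two measurements of the same quantity in the same unit. A walking speed and a sit-to-stand time do not qualify, so the sentence cannot be carried out literally for every pair of tests. Where it can be carried out, the source (LINQ, ActiGraph or CAREN) is open. So is the treatment of three 4MGS values per subject against one 6MW value. Two analysts could therefore produce different plots from the same plan.

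The word agreement adds a second worry. The tests have different instructions and settings, so true differences between them are expected. A reader who took cross-test limits as a measure of LINQ accuracy would be misled.

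**Working it through.** **Which pairs share a quantity.** Four maneuvers give 4 × 3 / 2 = 6 pairs. A pair counts if the endpoints in protocol C.2 and the descriptions in F.3 let both tests yield the same quantity in the same unit.

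| Reading of the parameters | Pairs with a shared quantity |
|---|---|
| Test results in their own units (time in FTSTS and ETGUG) | 1 of 6 |
| Gait speed from 4MGS, 6MW (distance / 360 s) and ETGUG walk | 3 of 6 |
| Gait speed, plus a stand-up measure from FTSTS and ETGUG | 4 of 6 |
| As above, plus one vertical-axis parameter from all four tests | 6 of 6 |

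Four is the most natural count. It assumes that the ETGUG phase data yield both a walking speed and a stand-up measure, and it leaves out 4MGS-FTSTS and 6MW-FTSTS. Correlation needs no common unit, so it can be computed for all six pairs.

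**What the repeats could change.** Let the difference for repeat k be D_k = B + W_k, with W_k independent between repeats, and let ICC be the share of the variance of D_k that is due to B. The SD for a mean of three relative to a single walk is sqrt(ICC + (1 − ICC)/3). The documents give no ICC, so a range is assumed:

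- ICC 0.3: sqrt(0.533) = 0.730, limits 27% narrower
- ICC 0.5: sqrt(0.667) = 0.816, 18% narrower
- ICC 0.7: sqrt(0.800) = 0.894, 11% narrower
- ICC 0.9: sqrt(0.933) = 0.966, 3% narrower

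The extremes are 0% at ICC 1 and 42% at ICC 0. The repeats are ordered in time and meant to show tiredness, so independent W_k is itself an approximation.

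**Against sampling error.** The approximate 95% half-width for one limit of agreement is t(n−1) × SD × sqrt(1/n + 1.96²/(2(n−1))). With n = 20 this is 2.093 × sqrt(0.0500 + 0.1011) = 0.81 SD. The limit lies 1.96 SD from the bias, so the half-width is 0.814/1.96 = 42% of that distance.

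**If 60 readings were pooled as independent.** The expected variance of 60 pooled readings is 1 − 2 × ICC/59 of the true single-walk variance. At ICC 0.9 that is 0.969, so the limits shrink by only 1 − sqrt(0.969) = 1.5%. Intervals suffer more. The half-width for a limit would be shown as 0.44 SD instead of 0.81 SD. In 20,000 simulated trials per setting, a nominal 95% interval for bias covered 88%, 83%, 79% and 75% at ICC 0.3, 0.5, 0.7 and 0.9, against 95% with subject means. Neither document plans such intervals.

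**What LINQ-only cross-test limits can show.** The between-test difference has variance SD_task² + 2 SD_e²(1 − ρ), where SD_e is the LINQ error SD (equal in both tests) and ρ the error correlation between tests. With limits of ±w and SD_task = 0, the largest possible SD_e is w/(1.96 × sqrt(2(1 − ρ))). This is 0.36w at ρ = 0, 0.51w at ρ = 0.5 and 1.14w at ρ = 0.9; the smallest is 0. A constant LINQ bias cancels if it is equal in both tests. The width alone is therefore no accuracy figure. The objective does not use it as one.

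**The case for a change.** The strongest case for a change is that it costs a sentence in two places. It would let a second statistician reproduce the plots, which matters because SAP 8 calls for results to be confirmed by one. SAP 6 speaks of reproducible results, and the cross-test comparison may be meant to serve that aim without saying so. The repeat gap also reaches the per-maneuver 4MGS comparison of LINQ with reference, so it cannot be confined to a side analysis. In addition, the 4MGS is nested in the 6MW, so that pair compares part of a walk with the whole.

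These facts stand, but they do not make a change necessary. The need for a shared unit decides which plots can be drawn, and gait speed is already named in the section. The stated reason for the repeats points to showing them in order, with a per-subject summary, rather than pooling them. SAP 7.4 requires the number in each analysis to be reported, and protocol H.1 requires changes of method to be justified in the report. A second statistician can confirm results against the choices recorded there.

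Tighter text also has limits. Only the sponsor knows the purpose of the comparison. A rule that LINQ error be read from the LINQ-versus-reference plots would be wrong, because those plots contain reference error too.

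**Conclusion.** No change follows. The sentence is underspecified, and the handling of the three 4MGS repeats is missing from both documents, including for the per-maneuver 4MGS analysis. This is the kind of detail that a competent analyst fills sensibly in a feasibility study of about 20 subjects with no hypothesis.

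The stated objective (protocol C.1.1, SAP 4) is LINQ against reference. Comparison between tests lies outside it, and no decision in the plan depends on it. The choice between single walks and subject means moves limits by 3% to 27% under the assumed ICC range, against a confidence half-width of about 42% of the distance from bias to limit. Unlike sampling error, the choice also changes what the limits describe, so the report should label which was used; that is ordinary reporting.

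The count of 4 in 6 pairs is an inference with a range of 1 to 6. The bounds on LINQ error depend on an error correlation that the documents do not give. The conclusion rests on none of these values. It rests on the descriptive role of the analysis and on the separate comparison of LINQ with reference for each maneuver.

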7.10. Safety Evaluation

Since the Reveal LINQ will not be used for medical purposes but exclusively for technical reasons and therefore it is considered a non-medical device in this study, no Safety outcomes analyses will be performed.

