### Devices used in the study

The following products will be worn externally by the patients to capture movement signal:

- 3-D accelerometer – ActiGraph™ wGT3X-BT
- Accelerometer - Reveal LINQ™ with software RAMware REEF Research System, Rev 1.0 onboard
- DR220 Holter

All medical devices used in this study are CE marked. The intended use of the Reveal LINQ in this study will not be for medical purposes, but exclusively for technical reasons, therefore the Reveal LINQ will be considered a non-medical device in this study. The Reveal LINQ device will be used externally, will have the investigational software RAMware REEF Research System, Rev 1.0 onboard. The software will be downloaded through the 2090 programmer. Since RAMware REEF Research System is an accessory to the Reveal LINQ it will also be classified as a non-medical device. Subjects will perform part (i.e. Six Minute Walk Test, 4 Meter Gait Speed Test) of the walking exercises inside the Computer Assisted Rehabilitation Environment (CAREN) system, to record additional subject position information.

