### Treatment

On arrival to the rehabilitation center subjects will have the Reveal LINQ, the 3D-accelerometers (one on the chest by medical-grade adhesives and a second at the level of the waist over the top of a medical grade adhesive) and the Holter attached externally. Then, they will be asked to perform the following exercises:

- Six Minute Walk (6MW) Test
- 4 Meter Gait Speed (4MGS) Test
- Five Times Sit to Stand (FTSTS)Test
- Expanded Timed Get-Up-and-Go (ETGUG) Test

Upon completion of the walking exercises, the Reveal LINQ device as well as the Holter and the Accelerometers will be removed from the subject and the subject's participation in the study will be complete. A Study Exit form will be completed.

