## B.2 Device information

No devices are implanted in this study. During the study visit subjects will be asked to wear the study device Reveal LINQ, with the REEF Investigational software installed, attached on the left hemitorax by medical-grade adhesives (i.e. Tegaderm, steri-strips).

Part of the walking exercises requested by the protocol will be performed within the Motek Medical CAREN (Computer Assisted Rehabilitation Environment) system. It is a hardware and software system for registration, evaluation and training of functional human behavior consisting of a motion base (with a dual belt instrumented treadmill), a camera real-time motion capture system, a projection screen and the D-flow software (<http://www.motekmedical.com/products/caren>).

Study Device:

- Reveal LINQ: A Medtronic, CE marked miniaturized insertable cardiac monitor (ICM) that is usually inserted subcutaneously through a minimally invasive procedure in patients with suspected arrhythmias for continuous monitoring of a patient's ECG and other physiological parameters.

In this study, the device will not be used according to its current indications. The Reveal LINQ will not be inserted subcutaneously, but will be worn externally on the chest and used as an accelerometer to register walking patterns. The same Reveal LINQ device will be worn externally by more than one subject and should be sanitized after each deployment as per common clinical practice.

Although the Reveal LINQ devices used in this study have engraved "Not for Human Use" as measure to prevent any accidental implantation, they are to be used in humans but not to be implanted. The parylene coating is removed due to the engraving. The Reveal LINQ package study specific labeling will be in English identifying the device as "Exclusively for Clinical Investigation - External use only". Furthermore, a medical-grade adhesive will be placed below the Reveal LINQ as an additional safety measure aiming to avoid direct contact with the titanium case of the Reveal LINQ and patient's skin. Since the purpose of this study is to investigate whether it is technically possible to obtain information about movement with the Reveal LINQ, the device will be considered a non-medical device.

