# **H DATA ANALYSIS AND REPORTING**

## **H.1 Analysis of clinical data**

Descriptive statistics will be used to summarize the patient demographic and clinical characteristics at baseline. Data for qualitative variables will be presented as prevalence rates (total number of subjects, number of events, and percent). Data for continuous variables will be summarized using measures of central tendency and dispersion.

All subjects who signed the informed consent document will be defined as the All Enrolled Population. The Analysis Population is defined as subjects who are enrolled and complete at least one of the walking exercises. Subjects who are enrolled but are found to have a protocol deviation such that the clinical interpretability of the results obtained from the patient is impacted, will not be included in the primary analysis, but will be reported in the patient disposition table. The analysis exclusion of subjects due to inclusion or exclusion criteria violation or a significant CIP deviation will be decided upon by the study team blinded without prior knowledge of statistical analysis results. Safety will be reported on the All Enrolled Population and the primary objective will be reported on the Analysis Population.

During the study all movement data is continuously collected. The primary endpoint for this study are the gait parameters obtained from the Reveal LINQ – REEF Research System, Rev 1.0 (accelerometer) and the external reference system (i.e. validation accelerometer and/or computer assisted rehabilitation system). All data processing will be performed offline.

The gait speed (and additional parameters) will be calculated from the Reveal LINQ accelerometer signals, from the validation accelerometer and/or from the computer assisted rehabilitation system. Correlation coefficients between the Reveal LINQ parameters and those from the reference system will be calculated for each maneuver (4MGS, FTSTS, ETGUG and 6MHW). The agreement between the Reveal LINQ derived parameters and the reference parameters will be reported and visualized using Bland and Altman plots.

The agreement between the parameters derived during the different maneuvers will also be evaluated using correlation coefficients and Bland-Altman plots.

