### J.2 Risks

Since the study devices will not be used for therapeutic purposes, but just to collect accelerometer data and considering the nature and duration of the study, no major risks to the subjects are expected with this study. It may be possible to anticipate local events at the level of the study tool/product placement (i.e. Allergic reaction, Skin irritation) - which the medical grade adhesive placed below the device should prevent - and/or events related to the physical execution (i.e. accidental fall) of the walking exercises.

Any further detail coming from risk assessment on potential risks and risks minimization will be provided under a separate cover.

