7.12. Changes to Planned Analysis

No major modifications are required from the analyses planned in the protocol.

8. Validation Requirements

To ensure the quality of the results provided for the study in the form of tables, listings and figures the following processes are used:

- Statistical analysis will be done by qualified MDT personnel following best practices.
- Statistical results will be reviewed and confirmed by a second MDT statistician or designee.

According to Medtronic SOPs the validation will be implemented for statistical outputs

9. References

1. <http://www.strobe-statement.org/index.php?id=available-checklist>

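### Protocol H.1 commits to reporting safety on all enrolled subjects, but SAP 7.10 plans no safety analysis and SAP 7.12 does not list this as a change

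*SAP*

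**What the plan says.** Protocol H.1 assigns the analyses to populations in one sentence: "Safety will be reported on the All Enrolled Population and the primary objective will be reported on the Analysis Population". The All Enrolled Population is everyone who signed consent. SAP 7.1.3 keeps that definition but calls the set the Full Analysis Set (FAS).

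SAP 7.10 then says that "no Safety outcomes analyses will be performed". The only reason given is that the Reveal LINQ serves a technical purpose and so counts as non-medical in this study. SAP 7.12 states: "No major modifications are required from the analyses planned in the protocol".

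The protocol already holds the same classification. Its synopsis says "therefore the Reveal LINQ will be considered a non-medical device in this study", section B.2 says "the device will be considered a non-medical device", and E.2.4 repeats the point.

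On risk, protocol J.2 expects nothing major. It does anticipate allergic reaction and skin irritation where study products are placed, and "events related to the physical execution (i.e. accidental fall) of the walking exercises". The Treatment part of the synopsis shows that the LINQ is not the only item attached: subjects also wear a Holter and two accelerometers, "one on the chest by medical-grade adhesives and a second at the level of the waist".

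Protocol F.7, headed for adverse events and device deficiencies, opens by saying that none of the sponsor's market-released devices in the study counts as a medical device. It then asks the investigator only for product complaints, including those about other manufacturers' devices.

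**The concern.** A report that the protocol commits to has no counterpart in the SAP. The reason given for leaving it out was available when the commitment was made, and it concerns one device rather than the study procedures. An analyst who follows the SAP will produce no account of the falls and skin reactions that the protocol itself anticipates. Someone who reads only 7.12 to learn what changed will not find this item.

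What is at stake is completeness of reporting and traceability between the two documents. The comparison of LINQ gait parameters with the reference systems does not depend on it.

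**Working it through.** No formula applies: the protocol gives no event rate, and the sample of about 20 has no power calculation behind it. The check is a comparison of text.

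1. **Is there a commitment?** Yes. H.1 says safety will be reported and names the population. It is the only analysis that H.1 assigns by name to the All Enrolled Population.

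2. **Did a later protocol withdraw it?** Nothing in the documents suggests so. The protocol's change history lists only version 1, and the SAP names version 1 as its basis.

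3. **Does another SAP section supply the report?** No. Section 7.1.1 covers disposition, 7.1.2 covers deviations, and 7.6 places baseline summaries on the Analysis Population. The 7.1.3 table, as read from the PDF, has columns for baseline and endpoints and none for safety; the conclusion does not depend on that table. An event that ended participation might surface as a reason in the disposition report. A fall or skin reaction in a subject who finished the tests has no planned output.

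4. **Is the reason new?** No. It stands in the synopsis, B.2 and E.2.4 of the protocol that contains H.1.

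5. **Does the reason cover the foreseeable events?**
   - Falls: no. J.2 ties them to performing the exercises, whatever the regulatory status of any device.
   - Skin reactions: only in part. J.2 speaks of placement of study products in general, although its remark about adhesive below the device points mainly to the LINQ. That the accelerometer and Holter sites are also exposed is an inference from the Treatment text. The synopsis lists these as study devices, and E.2.4 says the medical devices used in the study are CE marked, so the LINQ's classification does not extend to them.

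6. **Is the change listed?** Not in 7.12. SAP 7.11 makes a useful contrast: it leaves out health outcomes analyses because the protocol planned none. Section 7.10 could not give that reason.

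7. **Is the protocol consistent with itself?** No. H.1 promises a safety report, but C.2 has no safety endpoint, F.7 asks only for complaints, and neither Table 1 (data collection) nor Table 3 (data recorded directly on the CRF) has an event item.

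**The case against.** The strongest reply is that the SAP followed the protocol's own adverse-event section. F.7 relies on the non-medical status of the sponsor's device and asks for nothing beyond complaints, so the protocol points two ways and the SAP took one of them. This stands: the fault is shared, and H.1 and F.7 need attention as much as 7.10.

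A reader might infer that the omission was hidden. The documents do not support that. Section 7.10 states it openly with a reason, 7.12 speaks only of major modifications, and H.1 requires changes of method to be described in the clinical study report, not in the SAP. What remains is that 7.12 does not name a departure from an explicit commitment, which leaves the report's author without a prompt to justify it.

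A reader might also infer that safety will go wholly unreported. That goes too far: H.1 speaks of reporting and 7.10 of outcome analyses, so a narrative or complaint summary in the study report is not ruled out. Withdrawal reasons (F.8) and any safety reports the ethics committee imposes (E.2.1) are further routes. None of these, however, is a planned summary on all enrolled subjects.

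Finally, the study is a single visit with externally worn devices, and the protocol sees no safety concern that calls for a monitoring committee. That supports keeping any safety output simple, but does not resolve the contradiction.

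**Conclusion.** The point holds as a conflict of wording that needs reconciling. Protocol H.1 commits to a safety report on about 20 enrolled subjects. SAP 7.10 plans no safety analysis, for a reason that is neither new nor wide enough to cover falls or skin reactions at the other device sites, and 7.12 does not record the change. The protocol adds to the problem through F.7 and the lack of any event item in its endpoints and data tables.

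The size is modest. The agreement analysis is unaffected, and with no event rate in the documents the number of events that might go unreported cannot be estimated. It would be tempting to conclude that events in subjects who complete the tests are not captured at all. That cannot be determined: the case report forms, the Data Management Plan and the detailed risk assessment are separate documents not available here, and Study Exit forms are completed for finishers too. The conclusion assumes only that the SAP is carried out as written.

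**What to change.** Reconcile protocol H.1 and F.7 with SAP 7.10 and 7.12. There are two ways to do so.

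**Honour H.1.** Replace 7.10 with wording such as: *Falls, skin reactions at any device site, and other events already recorded on Study Exit forms, deviation forms or product complaints will be listed and counted descriptively on the FAS (All Enrolled).* Add safety to the 7.1.3 table for the FAS. State in the clinical study report how events were captured and, if capture was not systematic, that absence of reports is not evidence of safety.

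**Keep 7.10.** List the omission in 7.12 as a change from H.1 and justify it in the clinical study report, as H.1 requires for any change to the analysis methods.

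The first route costs a few lines of SAP text and one short listing with counts for about 20 subjects. Its drawback is that the listing may be incomplete. It needs no search of hospital charts, which the protocol's source table does not use for events, and no new data collection. The second route costs one declared and justified departure. If F.7 itself is reworded, that change follows the protocol's amendment procedure (E.2.1 and F.9.3).
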